An additional component of the study, which is entirely optional, is to obtain patient serum samples (about two teaspoons) in the operating room and 15 minutes and 4 hours after ketamine infusion. We will use these samples to assess levels of IL-1, IL-6, TNF- α , and BDNF, which are markers for pain. In addition, with patient consent, we will also store serum samples for future research use to measure other cytokines and neurotrophic factors and molecular markers associated with pain and depression.

Study site: Tisch Hospital

Outcome measures

Primary outcome measure: scores on the following questionnaires: 1) The Beck Depression Inventory (BDI); 2) Visual Analog Scale (VAS) score; 3) McGill's short form; 4) QoR-15 form; and 5) Montgomery-Asberg Depression Rating Scale (MADRS). The BDI and MADRS provide assessments for mood and function, VAS and McGill's assess pain, and QoR-15 assesses patient's overall satisfaction with postoperative recovery.

After consent is achieved in the pre-admission clinic prior to surgery, patients will be asked to fill out BDI, MADRS and QoR-15 forms to establish baseline scores. The BDI, MADRS will be filled out on postoperative days (POD) 0 after the infusion of ketamine, and BDI, MADRS and QoR-15 forms will be repeated on POD1, 2 and 7. McGill's short form will be filled out prior to discharge from the PACU and on POD 1, 2 and 7. VAS will be filled prior to PACU discharge, and every day while patient is in the hospital and on POD 7. VAS is a routine part of hospital care and will be administered daily whether a patient is enrolled in the study or not. If a patient has been discharged prior to POD2 or 7 (patients typically are discharged on POD2 or 3 in our practice), then a member of the study team will contact the patient by telephone to fill out these questionnaires.

Secondary outcome measures: 1) length of stay during hospitalization; 2) opioid usage per hour during the PACU stay before and after ketamine infusion; 3) opioid usage per day throughout the hospital stay; 4) time to out of bed to chair (OOB); 5) spirometry use 4 hours after the termination of ketamine infusion; 5) anti-emetic use in the PACU.

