Length of stay, opioid usage, and anti-emetic use will be recorded from electronic medical chart. Patient will be asked to record and report the time to OOB. Spirometry use will be assessed by a study team member to determine whether the patient is meeting the goal set by the surgical team 4 hours after ketamine infusion.

Exploratory secondary outcome measures: changes in serum levels of IL-1, IL6, TNF- α , and BDNF, which will be collected at baseline (in the OR preoperatively), and 15 min and 4 hours after the termination of ketamine infusion.

Study population

Inclusion criteria:

1. Adults, >18 years, <65 years, who will undergo gastric bypass or sleeve gastrectomy.
2. Subject is non-lactating and is either:
 - a. Not of childbearing potential; or
 - b. Of childbearing potential but is not pregnant at time of baseline as determined by pre-operative pregnancy testing.
3. Subject is ASA physical status 1, 2, or 3.
4. Subject who is deemed medically stable

Exclusion criteria:

1. <18 years of age; >65 years of age
2. Pregnant or breastfeeding
3. Does not speak or understand English (the study forms used are copy-right in English)
4. Cognitively impairment (by history) or clinical signs of altered mental status
5. History of misuse or abuse of ketamine
6. History of chest pain or chest pain in the PACU
7. Use of a medication that interferes with metabolism of ketamine within the last 24 hours
8. A diagnosis of schizophrenia and/ or a history of chronic antipsychotic medication use
9. History of head trauma
10. History of intracranial mass or hemorrhage
11. History of stroke
12. History of cardiac arrhythmia
13. Subject for whom ketamine is contraindicated
14. Unwillingness to give informed consent according to HIC guidelines

Entry into Study

Flyers will be designed and posted in the bariatric clinic as well as the pre-admissions testing (PAT) clinic to inform patients about this study. Patients will be recruited from the bariatric clinic during their visit with the pre-surgical clinic visit with their surgeons, from the PAT during their preadmission visit, or from the holding area on the day of surgery. Researchers will hold a general discussion with interested patients regarding the study. The patient may have family included, if he/she prefers. We will be approaching all subjects (male and female) who are undergoing laparoscopic gastric bypass or sleeve gastrectomy.

Pre-Study Screening

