Potential subjects will have an initial pre-study screening, conducted by a member of the research team, to determine eligibility for the study. Potential subjects who are non-English speaking will be automatically excluded, because the questionnaires are copyrighted in English only. Subjects who do not have the capacity to consent will not be recruited. All other subjects will be recruited. For any patient who might be illiterate, consents will be read to him or her and witnessed by available staff or family member.

Informed Consent

Eligible patients will be assessed for capacity to give informed consent by a study team member. Medical clearance/status/stability will be addressed by members of the research team. Eligible patients will be invited to participate in the study. A verbal explanation of the study will be given followed by a written consent form. Study staff members are experienced at consenting patients for anesthesiology studies, and they include physicians as well as research associates.

[figure not shown]
Intervention Administration

Ketamine bolus doses of 0.4 mg/kg (by ideal body weight) will be prepared and stored by the Pharmacy staff at Tisch Hospital and will be delivered to the PACU on an on-call basis when required for a study subject. The study drug will be administered in accordance to best practices. Ketamine will be given via intravenous infusion through an IV line established in the PACU. All patients will have an IV line in the PACU as per standard postoperative care protocol after bariatric surgery. If necessary, an additional IV line will be placed by the study team for the infusion of the study drug. The study drug or control will be administered over <60 minutes. The dose for ketamine will be fixed at 0.4 mg/kg (ideal body weight). The staff administering the infusion will have no knowledge whether the agent is drug or saline control. The patient will be monitored in the PACU according to the standard PACU protocol. In addition, the patient will be monitored for any potential side effects of the medication, which include hypertension, tachycardia, nystagmus, perceptual disturbances, confusion, sedation, euphoria, dysphoria, and dizziness. These side effects are uncommon, and a majority of these side effects are expected to resolve shortly after infusion.¹³ Side effects will be documented and treated if necessary as per standard PACU protocol.

Study drug storage

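### Post-infusion opioid rate and anti-emetic use are measured up to PACU discharge, a time the study drug could shift; a fixed window from the end of infusion would avoid this at little cost (low severity)

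*Combined protocol and SAP*

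**What the plan says.** The Outcome measures section lists six secondary outcomes. Two are tied to the PACU: "opioid usage per hour during the PACU stay before and after ketamine infusion" and "anti-emetic use in the PACU". Specific aim 1 under Study Objective repeats the opioid measure. Neither is given a fixed post-infusion interval. No section gives PACU discharge criteria, lists PACU duration as an outcome or adjusts for it; the length-of-stay outcome refers to the hospitalization.

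Two other secondary outcomes bear on the point. One is "opioid usage per day throughout the hospital stay", which does not depend on when the patient leaves the PACU. The other is "spirometry use 4 hours after the termination of ketamine infusion", which has a fixed clock time; the second post-infusion serum sample uses the same 4-hour anchor. On data source, the plan says: "Length of stay, opioid usage, and anti-emetic use will be recorded from electronic medical chart".

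Intervention Administration names the effects to be watched for in the PACU, "which include hypertension, tachycardia, nystagmus, perceptual disturbances, confusion, sedation, euphoria, dysphoria, and dizziness", and adds: "Side effects will be documented and treated if necessary as per standard PACU protocol". Between those two statements it says that the effects are uncommon and that most should pass soon after the infusion. It allows up to an hour for the infusion. The plan does not say whether infusion time belongs to the period before or after.

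**The concern.** The post-infusion opioid rate is the opioid given after the infusion divided by the remaining PACU hours. The assigned treatment may influence those hours: sedation, confusion or dizziness could delay discharge, and better pain control could bring it forward. Randomization makes the arms comparable at dosing. It does not protect a denominator that is set afterwards.

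Dividing by hours corrects for unequal stay only if need is constant over the stay. If need falls, a longer window averages in low-need hours and the rate drops even when opioid use is identical at every time point. A shorter window does the reverse and could hide real sparing. Anti-emetic use has no time scaling, so more hours give more opportunity for a dose. The profile of the study drug also lists nausea and vomiting as ketamine effects, so a true increase and a longer exposure could not be told apart.

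A lower opioid requirement is one of the hypotheses in Study Rationale, so the opioid rate bears on a claim the trial intends to make.

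**Working it through.** **The plan's own figure.** The only computed design figure is 50 per arm (Sample Size Justification), for a 22.5% difference, SD 40%, power 0.8 and type I error 0.05. Two-sided, n = 2 × (1.960 + 0.842)² × 40² / 22.5² = 49.6, so 50 per arm reproduces. It is based on psychometric scores and is unaffected by this point. No figure is given for the opioid or anti-emetic outcomes.

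**Inputs.** From the documents: 50 per arm and type I error 0.05. Assumed, because the documents are silent: a 2-hour remaining PACU stay after infusion, the time course of opioid need, the extra stay under ketamine, and an opioid coefficient of variation (CV) of 0.8.

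**Step 1: shift when every ketamine patient's stay changes.** Opioid need over time is identical in both arms. If need halves every h hours, the mean hourly rate over T hours, relative to the starting rate, is (1 − e^(−kT)) / (kT), with k = ln 2 / h. For h = 1 this is 0.541 at 2 h and 0.475 at 2.5 h, a ratio of 0.878, or −12%.

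| Assumed need | 1.5 h vs 2 h | 2.5 h vs 2 h | 3 h vs 2 h |
|---|---|---|---|
| Halves every 1 h | +15% | −12% | −22% |
| Halves every 2 h | +8% | −7% | −14% |
| Halves every 4 h | +4% | −4% | −8% |
| Constant | 0% | 0% | 0% |
| Rises each hour by 25% of starting rate | – | +5% | +10% |

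The sign depends on both the direction of the stay difference and the course of need.

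**Step 2: shift when only some patients stay longer.** If a fraction f stays 60 minutes longer, the mean shift is f times the last column.
- f = 0.10: 0.10 × 7.7% = 0.8% to 0.10 × 22.2% = 2.2%.
- f = 0.20: 0.20 × 7.7% = 1.5% to 0.20 × 22.2% = 4.4%.

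**Step 3: chance of a significant result from that shift alone.** With shift d, z = d / (CV × √(2/50)), which is d / 0.16 at CV 0.8. The rejection probability is Φ(z − 1.96) + Φ(−z − 1.96).
- Everyone 30 minutes longer: d = 4.0% gives z = 0.25 and 5.7%; d = 12.2% gives z = 0.76 and 12%.
- 20% of patients 60 minutes longer: d = 1.5% to 4.4% gives 5.1% to 5.9%.
- 10% of patients 60 minutes longer: d = 0.8% to 2.2% gives 5.0% to 5.2%.
- Everyone 60 minutes longer with need halving hourly: d = 22.2% gives z = 1.39 and 28%.

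A smaller CV raises these. At 0.4 (the plan's SD for psychometric scores, not opioid use), the 20% case with d = 4.4% gives z = 0.044 / 0.08 = 0.56 and about 8.6%.

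**Step 4: anti-emetic use.** The plan does not say whether this is any use or number of doses. For illustration, with any use and an assumed constant hazard of 0.1 to 0.3 per hour, the proportion is 1 − e^(−hazard × T): 18% to 45% at 2 h and 26% to 59% at 3 h. If only 10-20% stay the extra hour, the arm difference is 0.10 × 7.8 = 0.8 to 0.20 × 14.2 = 2.8 percentage points, against ketamine.

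**Step 5: fixed window.** When T is the same in both arms, the shift from unequal observation time is 0% for every time course above.

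**The case against.** The strongest reply is that the per-hour scaling already allows for unequal PACU time, and that nothing in the documents shows the stay will differ by arm. The plan's only statement on the frequency and duration of side effects points to a small effect. This largely stands. It makes a uniform 30- or 60-minute delay an upper scenario and the 10-20% scenario the closer reading.

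A reader might infer more than the documents support:
- That a longer stay by itself lowers the opioid rate. It does so only if need is falling. That is plausible after surgery, but the documents give no time course; under constant need there is no bias, and under rising need it reverses.
- That ketamine prolongs the PACU stay. No section says so, and a shorter stay is also possible.
- That a false opioid-sparing result is likely, at about 28%. That figure needs every ketamine patient delayed by an hour and need halving hourly.
- That anti-emetic use is biased in ketamine's favor. A longer stay would count against it.

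These are also secondary outcomes outside the sample-size calculation, and daily opioid use gives the opioid hypothesis a second measure. That limits the harm. But the daily measure covers a different period, so it is only a partial check on a PACU result. Finally, a fixed-window total answers a slightly different question because it mixes PACU and floor care. That is fair, and is a reason to keep the PACU rate as a supporting measure.

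**Conclusion.** The point holds in limited form, with low severity. Both outcomes end at a post-dosing event that treatment could move, and the plan neither fixes the window nor records PACU duration as an outcome. The direction of any opioid bias cannot be settled from the documents.

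Under the stated assumptions (2-hour window, need halving every 4 to 1 h, CV 0.8, 50 per arm), a 30-minute delay for every ketamine patient would lower the rate by about 4-12%. A 60-minute delay for 10-20% of them would lower it by about 1-4%, with false rejection about 5-6%. The second scenario fits the plan's description of side effects better. The pre-infusion rate cannot be affected by the assigned treatment, and no primary outcome is involved. The case for change rests on low cost and clearer interpretation, not on a large expected bias.

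**What to change.** Define post-infusion opioid use as the total dose, in one opioid-equivalent unit, over a common fixed interval from the end of infusion. An example is 0-4 h, which matches the spirometry and serum anchor. Count anti-emetic doses over the same interval. Take both from the electronic chart wherever the patient is, and state whether infusion time counts as before or after. Report PACU duration by arm, and keep the PACU hourly rate as a descriptive or supportive measure.

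The cost is revised outcome wording and a defined abstraction window in a chart already being used. Patient care does not change. The downside is that some windows will include doses from the floor chart. Because the plan expects discharge from hospital on day 2 or 3, a 4-hour window should normally fall within the stay.

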Ketamine, given for postoperative pain control, can be hypothesized to have long lasting analgesic effects as well as effects on improving mood and function in the postoperative period. Ketamine can be administered as a single dose in the post-anesthetic care unit (PACU), where patients are closely monitored for potential side effects. We hypothesize that postoperative use of ketamine should lead to improvement in pain indices including visual analog scale (VAS), a decrease in opioid requirement, mood improvements as measured by psychometric indices, and finally improvements in functional measures including early mobility and faster discharge from the hospital. In addition, we will assess serum levels of IL-1, 6, TNF- α , and BDNF to see if alterations in levels of cytokines and neurotrophic factors occur with postoperative pain and how ketamine treatment may influence the levels of these biomarkers.

Study Objective

Specific aim 1: examine the effect of a single, subanesthetic dose (0.4mg/kg) of ketamine vs. saline control on mood and postoperative function in patients who have undergone gastric bypass and sleeve gastrectomies.

Pain relief and changes in postoperative mood and function will be assessed using both patient report, in the forms of a series of questionnaires, and medical chart review. The questionnaires we use will be Beck Depression Inventory (BDI), Visual Analog Scale (VAS), McGill's short form, QoR-15 form and the Montgomery-Asberg Depression Rating Scale (MADRS). Please see below for a detailed discussion of these forms. In addition, from the chart review we will monitor length of stay during hospitalization, opioid usage per hour during the PACU stay before and after ketamine infusion, total opioid usage per day throughout the hospital stay, time to out of bed to chair, and spirometry use after ketamine infusion.

Specific aim 2: examine the effect of a single, subanesthetic dose (0.4mg/kg) of ketamine vs. saline control on inflammatory cytokines and neurotrophic factors in the postoperative period.

We will examine the effect of ketamine on proinflammatory markers and neurotrophic factors known to be linked with pain. We will examine levels of interleukin factor 1 and 6 (IL-1, IL-6), TNF- α , and BDNF. This aim will provide potential mechanism of action for ketamine.

Overall study design and plan

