This is a randomized, double-blind, placebo-controlled, two-arm parallel, single-center study. One hundred subjects (50 in each arm) will be enrolled. Subjects, between the ages 18 and 65, undergoing laparoscopic gastric bypass or sleeve gastrectomy under general anesthesia will be screened for eligibility to participate in the study. Subjects will be screened, recruited and consented during the preadmission visit prior to surgery. Eligible subjects will be randomized to one of the two treatment group in a 1:1 ratio to receive either IV ketamine (0.4mg/kg) or matching placebo. Both men and women will be recruited, and there is no limitation as to racial and ethnic origin.

Participation in the study will not alter the patient's surgical or anesthetic care, post-anesthetic care, or care on the floor. In the PACU, patients, if deemed medically stable by the study physician, will receive either 0.4mg/kg IV ketamine or placebo. All patients will also receive standard post-anesthetic monitoring and care, as well as routine care after transfer out of the PACU. There is no restriction on the use of other analgesics throughout the hospital stay. Patients are followed until the date of discharge, and endpoints (see below) are collected from patient reports as well as from medical charts. During their hospital stay (and once after their discharge from the hospital), patients will fill out five questionnaires which provide estimates of their postoperative pain control, mood and function, and quality of postsurgical recovery.

Patients will be randomized using a block randomization code for assigning 100 subjects to two groups. In Excel we generated 100 random numbers. In the next column we inserted multiple copies of the sequence PCPC where p= "placebo" and c = "control", forming 25 blocks. Then we sorted the random numbers in each 4 subject block, including the assignment letters (P, C) in the sort. The remaining list of Ps and Cs is the randomization.

To check the balance, we then did running counts of the cumulative repeats of "p" and "c" and "p - c". The tally for each totaled 50 and the two groups were always within 2 counts of being perfectly balanced, which met our goal. The list can be extended at will to accommodate screening failures.

Randomization lists will be sent to the pharmacy who will then be able to distribute the study drug/placebo as patients are enrolled and undergoing surgery, and the remainder of the study staff will be blinded.

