Sample Size Justification: Previous studies on the antidepressant effects of ketamine on depressed patients typically yield a mean difference in psychometric measures of 40%, with a standard deviation of roughly 40% as well. Power analysis yields $n = 50$ patients in each arm. This will allow for us to detect a true difference in the mean value of our outcome variable of $\pm 22.5\%$ with a probability (power) of 0.8. The type I error probability associated with this test of the null hypothesis that the population means of the ketamine versus control groups are equal is 0.05.

Statistical Analysis: For this study, descriptive statistics will be performed for all data and subgroups as needed:

- 1) Outcome tests (see above), N (%) for each category, showing absolute values, absolute

and percent differences, stratified by treatment etc.

- 2) Demographics showing continuous parameters (age, height, weight, etc.) as mean + SD; categorical parameters, as N (%); all also stratified by treatment.

Analysis of variance (ANOVA) test with repeated measures will be performed to determine within-patient effects (time) and between patient effects (treatment) on outcome measures. Pearson correlation will be used to assess relationships between continuous variables, and Spearman's Rho will be used for ranked data. For non-normally distributed, the Kruskal-Wallis test will be used for global significance, and Mann Whitney for subsequent pairwise comparisons.

Exploratory analysis will fit continuous (VAS score, length of stay in the hospital) and categorical (ordinal outcome data) to a Logistic Regression model which predicts the treatment bivariate (IV ketamine or placebo).

Interim Data analysis: An interim data analysis will be performed after a total of 50 patients have completed the study. An analysis of primary and secondary endpoints will be analyzed, and if the primary endpoints are met, we will opt to terminate the study.

DATA SAFETY AND MONITORING PLAN

Timeline

- 1) Estimated start date: Sept 1, 2013
- 2) Estimated time for start-up: 2 months
- 3) Time allotted for enrollment: 2 years
- 4) Estimated study end date: August 30, 2015

Data acquisition and management

The research material obtained from human subjects in this proposed study will be collected solely for research purposes. It will be as follows:

- a. *Clinical information* obtained by medical history, questionnaires and interviews.

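### The pre-infusion PACU opioid rate is listed within an outcome and not as a baseline, and the treatment effect the plan names would, if applied to both periods, halve any post-infusion difference

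*Combined protocol and SAP*

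**What the plan says.** The Outcome measures section gives, as the second secondary outcome, "opioid usage per hour during the PACU stay before and after ketamine infusion". Specific aim 1 under Study Objective lists the same item for chart review: "opioid usage per hour during the PACU stay before and after ketamine infusion, total opioid usage per day throughout the hospital stay". Neither place calls the earlier rate a baseline.

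The timing of treatment is in Overall study design and plan: "In the PACU, patients, if deemed medically stable by the study physician, will receive either 0.4mg/kg IV ketamine or placebo". The PACU period before the infusion is therefore untreated in both arms.

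Elsewhere the protocol names a baseline when it wants one. For the questionnaires, "patients will be asked to fill out BDI, MADRS and QoR-15 forms to establish baseline scores". For the serum markers, the first sample is one "which will be collected at baseline (in the OR preoperatively".

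The Statistical Analysis section, which appears again in the Data Safety and Monitoring Plan, gives one general model: a repeated-measures ANOVA "to determine within-patient effects (time) and between patient effects (treatment) on outcome measures". It names no treatment-by-time interaction, change score or baseline covariate. For non-normal data, "the Kruskal-Wallis test will be used for global significance, and Mann Whitney for subsequent pairwise comparisons". An exploratory logistic regression is also mentioned, but the continuous variables it names are VAS score and length of stay, not opioid use.

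**The concern.** A rate recorded before the study drug is given cannot respond to it. Its proper use is as a baseline that explains part of the variation between patients. If it is treated instead as the first of two repeated outcomes, the between-patient treatment term of the ANOVA compares patient averages over an untreated and a treated period, and the difference of interest is diluted.

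This matters because a lower opioid requirement is one of the hypotheses in Study Rationale, and the Background section gives opioid respiratory depression in bariatric patients as a reason for the trial. A diluted test could miss a real effect on this outcome. An unspecified test also leaves the choice of comparison open until the data have been seen.

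**Working it through.** **Inputs from the documents.** 50 per arm, 1:1; detectable difference 22.5%, SD 40%, power 0.80, type I error 0.05 (Sample Size Justification). Two-sided testing is taken from the null of equal means and the ± difference. The 40% mean difference in the same paragraph serves as a second effect size. These figures describe psychometric measures. The documents give no effect size, SD or pre/post correlation for opioid use, so they are borrowed here as an illustration.

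**Assumptions.** One pre-infusion and one post-infusion rate per patient, equal SDs (σ = 40), correlation ρ from 0 to 0.9, and no expected difference between arms before the infusion.

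**Step 1: the plan's own figure.** n = 2 × (1.960 + 0.842)² × (40/22.5)² = 2 × 7.85 × 3.16 = 49.6, or 50 per arm. Power at 50 per arm: SE = 40 × √(2/50) = 8.0; 22.5/8.0 = 2.81; Φ(2.81 − 1.96) = 0.80. The stated sample size is reproduced.

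**Step 2: what each analysis tests.** For a true post-infusion difference δ:

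| Analysis | Expected difference | SD per patient |
|---|---|---|
| Treatment main effect over both periods | (0 + δ)/2 = δ/2 | σ√((1+ρ)/2) |
| Post-infusion rate only | δ | σ |
| Treatment-by-time (same as change score) | δ | σ√(2(1−ρ)) |
| ANCOVA on the pre-infusion rate | δ | σ√(1−ρ²) |

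The halving in the first row is algebra and does not depend on ρ.

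**Step 3: power.** Power = Φ(difference/SE − 1.96), with SE = SD × √(2/50) = 0.2 × SD. Worked at δ = 22.5, ρ = 0.5:

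- Main effect: SD = 40√0.75 = 34.64, SE = 6.93, 11.25/6.93 = 1.62, power Φ(−0.34) = 0.37.
- Post-only: as in step 1, 0.80.
- Treatment-by-time: SD = 40√1 = 40, so again 0.80.
- ANCOVA: SD = 40√0.75 = 34.64, SE = 6.93, 22.5/6.93 = 3.25, power Φ(1.29) = 0.90.

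| Assumed ρ | 0 | 0.3 | 0.5 | 0.7 |
|---|---|---|---|---|
| Treatment main effect | 0.51 | 0.42 | 0.37 | 0.33 |
| Post-only | 0.80 | 0.80 | 0.80 | 0.80 |
| Treatment-by-time | 0.51 | 0.66 | 0.80 | 0.95 |
| ANCOVA | 0.80 | 0.84 | 0.90 | 0.98 |
| Loss, main effect against post-only | 36% | 48% | 54% | 59% |

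The loss is 1 − (main effect/post-only); at ρ = 0, 1 − 0.511/0.803 = 36%. Simulation at ρ = 0.5 gave 0.362, 0.798, 0.792 and 0.893 for the four analyses in the order of the table.

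**Step 4: the larger effect.** With δ = 40, post-only power is Φ(40/8 − 1.96) = 0.999. Main-effect power is Φ(20/5.66 − 1.96) = 0.94 at ρ = 0 and Φ(20/7.80 − 1.96) = 0.73 at ρ = 0.9. The loss is 6% to 27%.

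**Step 5: ANCOVA against the alternatives.** Because 1−ρ² = (1−ρ)(1+ρ) is below 2(1−ρ) whenever ρ < 1, ANCOVA has a smaller variance than the change score under equal SDs. Because 1−ρ² ≤ 1, it is also never worse than post-only, apart from one degree of freedom.

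**The case against.** The strongest reply is that the plan never assigns the treatment main effect to this outcome. Its ANOVA sentence is generic. Splitting the rate at the infusion suggests that a before-and-after comparison was in mind, and a two-arm, two-time ANOVA ordinarily produces a treatment-by-time term, which avoids the dilution. Opioid rates may well be skewed, in which case the plan turns to rank tests, and a Mann-Whitney test on the post-infusion period would not be diluted either. All of this stands. It makes the fault as much an unspecified analysis as a wrong one. It does not close the gap, because the plan names neither the interaction nor the value that the rank test would use. Treatment-by-time is also no better than post-only when the correlation is 0.5 or less.

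A reader might go further and infer that the trial loses over half its power on this outcome. The documents do not support that as a general statement. At the 22.5% difference, the loss passes one half only if the correlation exceeds about 0.35 (against post-only) or 0.29 (against ANCOVA). At a 40% difference, it stays at or below 27%. Both effect sizes are borrowed from another kind of measure.

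Nor do the documents show that the pre-infusion rate is a strong predictor. They give no length for the pre-infusion period, and a rate over a short or variable window could correlate only weakly with later use.

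**Conclusion.** The point holds as a gap in specification with a foreseeable cost. A pre-treatment value sits within an outcome without being designated a baseline, and the one between-arm effect that the ANOVA names would halve the post-infusion difference if applied to both periods.

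The halving is certain under that reading; the power loss is conditional. It is about 36-59% against post-only for correlations of 0 to 0.7 at a 22.5% difference, and 6-27% for correlations of 0 to 0.9 at a 40% difference. Both ranges rest on psychometric figures, equal SDs and 50 per arm. At a correlation of 0.5, the analyses compared here run from power 0.37 to 0.90, which is reason enough to prespecify one.

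The scope is one secondary outcome. The sample size is not based on it, and nothing here bears on the primary questionnaires.

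**What to change.** In Outcome measures and Specific aim 1, define the outcome as the post-infusion PACU opioid rate per hour, and move the pre-infusion rate from the outcome list to a named baseline covariate. In both copies of Statistical Analysis, state that the arms are compared on this outcome by ANCOVA with the pre-infusion rate as covariate, on a log or rank scale if the data are skewed.

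The cost is a few lines of text. Opioid use is already taken from the electronic chart, so no new data are needed. The gain over post-only is small if the pre/post correlation is low (0.80 to 0.84 for correlations of 0 to 0.3 in the illustration) and larger if it is high, and under the stated assumptions there is essentially no loss of power.
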